Patients who are at risk of TLS as determined by the treating physician, may receive Allopurinol 300 mg/day (or an equivalent standard agent for prevention of hyperuricemia) orally for the first two weeks of the first cycle of protocol therapy. Allopurinol may be continued after the first two weeks at the investigator's discretion and as clinically indicated. Subjects should be observed closely for signs and symptoms of TLS during the initial cycle of therapy. Subjects should be encouraged to drink an abundant amount of fluid prior to treatment. Subjects should maintain adequate hydration and urine output.

9.4 Treatment related lymphocytosis:

Lymphocytosis has been reported with ibrutinib, however since in this clinical trial patient will have received daratumumab prior to initiating the ibrutinib it is not known if this lymphocytosis will still happen upon treatment with ibrutinib. Patients who develop this reaction will be monitored as per standard clinical protocol without specific intervention unless other specific symptoms / signs of disease progression is noted (such as increase in lymph node size that is progressive and persist beyond 3 months of therapy, worsening of cytopenia from the time of initiation of therapy that is considered to be due to progressive disease and is consistent with the IWCLL guidelines requiring therapeutic intervention, development of B symptoms persisting for more than 2 months while on therapy or other factors such as organomegaly demonstrating disease progression).

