11.0 Treatment Evaluation/Measurement of Effect

Formal response evaluation should occur every 3 treatment cycles as per standard clinical practice. However, first response evaluation will occur at the end of 4 treatments of daratumumab (completion of cycle 1). This will allow correlation of the clinical activity of the single agent daratumumab with the correlative studies planned. Thereafter the clinical response will be evaluated after completion of every 3 cycles during combination therapy. Objective status should be classified as PD vs. Not PD on cycles when a formal response evaluation does not occur.

Patients will also be assessed as MRD^+ vs MRD^- (See section 11.4). Prior to the response evaluation (after 3 cycles of the combination), baseline on study measurements will be used to determine disease progression (e.g. not cycle by cycle comparisons). Once patients undergo formal response evaluation, the nadir value at either baseline or time of response evaluation will be used for evaluating future disease progression. In addition to a baseline scan, confirmatory scans should also be obtained as needed to document objective response at sites of non-palpable lymphadenopathy or organomegaly as indicated in Section 4 or as needed clinically.

NOTE: Information from CT scans is not considered in the standard classification of response.

Note: Treatment-related lymphocytosis is a known phenomenon with ibrutinib and is not representative of PD. As noted in the Leukemia Research Foundation Workshop report⁶²: "Patients with lymphocytosis and no other evidence of PD should continue therapy until they develop other definitive signs of PD (i.e., at least one feature suggesting worsening of the CLL other than lymphocytosis (e.g., anemia, thrombocytopenia, lymphadenopathy, or hepatosplenomegaly) or the occurrence of another reason to discontinue therapy."

PD: "If PD is suspected, clinical examination, computed tomography, and peripheral blood counts should be obtained, and a bone marrow biopsy considered, to provide objective assessment of CLL status. Similarly, persistent lymphocytosis should not interfere with the time of designation of a PR, which should be based more on the other measurable aspects of the disease than on lymphocytosis."

11.1 Schedule of Evaluations:

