11.226 Hemoglobin $>11.0 \text{ gm/dl}$ or 50% increase over baseline without transfusions.

11.227 For patients whose only measurable disease at the time of enrollment is on CT scan, a CT scan demonstrating $> 50\%$ reduction of target nodes enlarged at baseline is required before classifying patients a PR.

11.23 **PROGRESSION (PD):** Patients will continue to receive protocol therapy unless they have evidence of disease progression according to the IWCLL criteria⁶ as evidenced by:

11.231 $\geq 50\%$ increase in the sum of the products of at least 2 lymph nodes on 2 consecutive determinations 2 weeks apart (at least one node must be ≥ 2 cm) or the appearance of new palpable lymph nodes >1.5 cm not due to a tumor flare. Enlargements or the appearance of new nodes due to a tumor flare do NOT qualify as progression.

11.232 $\geq 50\%$ increase in the size of the liver and/or spleen as determined by measurement below the respective costal margin on 2 consecutive determinations 2 weeks apart and with a minimum of a ≥ 2 cm increase in size from baseline; or appearance of hepatomegaly or splenomegaly which was not previously present at baseline and not due to a tumor flare.

11.233 Transformation to a more aggressive histology (e.g. Richter's transformation).

Note: If a patient develops DLBCL at any time, it will be considered disease progression. If the patient develops any other hematologic malignancy while on study, it will not be considered progressive disease.

11.234 $\geq 50\%$ increase in the absolute number of circulating lymphocytes NOT due to infection or tumor flare (taking as reference for progressive disease the smallest absolute lymphocyte count recorded since the treatment started). The absolute lymphocyte count must be at least 5000/mm³ to qualify as disease progression.

11.235 In the absence of progression as defined by 1, 2, 3, or 4 above, the presence of a ≥ 2 g/dl decrease in HGB, or $\geq 50\%$ decrease in platelet count, or absolute neutrophil count will NOT exclude a patient from continuing the study. Work-up of such decreases to exclude autoimmune hemolytic anemia, pure red cell aplasia, or idiopathic thrombocytopenic purpura (ITP) should be considered.

11.236 For patients who achieve a CR or nodular PR, progression will be defined as recurrence of circulating leukemia cell clone and an ALC >5000 or recurrence of adenopathy >1.5 cm not due to a tumor flare.

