11.4 Summary Definition of objective response for patients with B-CLL

	CCR ¹	CR ²	CR ³	nPR ⁴	PR ⁵	PD ⁶
PHYSICAL EXAMINATION						
Nodes ⁷	None	None	None	None	<50%	>50% increase, new nodes
Liver/spleen ⁸	Not palpable	Not palpable	Not palpable	Not palpable	<50%	>50% increase, newly palpable
Symptoms	None	None	None	None	N/A	N/A
PERIPHERAL BLOOD						
ANC	>1500/ μ L	>1500/ μ L	See footnote 3	>1500/ μ L or >50% improvement from baseline	>1500/ μ L or >50% improvement from baseline	See footnote 6
Platelets	>100,000/ μ L	>100,000/ μ L	See footnote 3	>100,000/ μ L or >50% improvement from baseline	>100,000/ μ L or >50% improvement from baseline	See footnote 6
Hemoglobin	>11.0 g/dL without transfusion	>11.0 g/dL without transfusion	See footnote 3	>11.0 g/dL or >50% improvement from baseline without transfusion	>11.0 g/dL or >50% improvement from baseline without transfusion	See footnote 6
Lymphocytes	<4000/ μ L	<4000/ μ L	<4000/ μ L	<4000/ μ L	≥50% decrease	>50% increase to at least 5,000/ μ L
BONE MARROW	N/A	Normocellular ³ ; <30% lymphocytes; no nodules	<30% lymphocytes; no nodules	<30% lymphocytes; bone marrow nodules ⁴	N/A	N/A

1. Clinical complete response (CCR) requires fulfillment of all physical exam and peripheral blood criteria as noted in the table above. No bone marrow biopsy is required to call a patient a CCR; however, patients should have a bone marrow analysis performed within two month of the formal response evaluation where clinical and laboratory evidence of complete response was first seen as instructed in the test schedule to confirm CR as per standard guidelines by the IWCLL.
2. Complete response (CR) requires fulfillment of all physical exam and peripheral blood criteria for a duration of ≥2 months. A bone marrow aspirate and biopsy are required to document the response as a complete within two month of the formal response

evaluation where clinical and laboratory evidence of complete response was first seen (see Section 11.21).

3. Patients who fulfill all criteria for a CR but who have a persistent anemia, thrombocytopenia, or neutropenia related to drug toxicity rather than residual CLL or have hypocellular marrow will be classified as CR with incomplete marrow recovery(CRi).

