4. Nodular partial response (nPR) is essentially a patient who appeared to have a CR but nodules were present in the bone marrow. It requires fulfillment of all physical exam and lymphocyte criteria for CR; however, when the bone marrow is done to confirm CR, nodules of malignant lymphocytes are found. Patients must fulfill one or more of the blood count parameters (ANC, Platelets, Hemoglobin) but are not required to meet all 3 of these conditions. See Section 11.215 regarding the distinction between clonal and regenerative nodules.
5. Partial response (PR) requires fulfillment of at least two of the above-noted decrease in circulating lymphocytes, regression in adenopathy and regression in hepatosplenomegaly, and at least one other parameter listed above for a duration of ≥ 2 months. See Section 11.22.
6. Progression: Fulfilling the criteria as noted in section 11.23. Prior to the formal response evaluation, baseline on study measurements will be used to determine disease progression (e.g. not cycle by cycle comparisons). Once patients undergo formal response evaluation, the nadir value at either baseline or time of response will be used for evaluating future disease progression. In the absence of other indices of clinical progression, the presence of a ≥ 2 g/dL decrease in hemoglobin or a $\geq 50\%$ decrease in platelet count and/or absolute neutrophil count will not exclude a patient from continuing on the study. Although not mandatory, bone marrow aspirate and biopsy are strongly encouraged to better define the cause of the suppressed counts (e.g., treatment versus disease-related).

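### In patients with ibrutinib-related lymphocytosis, Sections 9.4 and 11.0 take CLL-attributed cytopenia (9.4 also persistent B symptoms) as progression, but Section 11.23 and the Section 11.4 table do not, so the PFS event depends on which section the assessor follows

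*Combined protocol and SAP*

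**What the plan says.** Two places describe progression in a patient who has treatment-related lymphocytosis.

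- Section 11.0 says that such a patient stays on therapy until other definitive signs of progression appear, and explains these as "at least one feature suggesting worsening of the CLL other than lymphocytosis (e.g., anemia, thrombocytopenia, lymphadenopathy, or hepatosplenomegaly". One feature is enough.
- Section 9.4 says that the reaction is only monitored unless other signs of progression are seen. Its list includes "worsening of cytopenia from the time of initiation of therapy that is considered to be due to progressive disease" (and consistent with the IWCLL indication for treatment) and "development of B symptoms persisting for more than 2 months while on therapy".

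The endpoint definitions read differently.

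- Section 11.23 opens with "Patients will continue to receive protocol therapy unless they have evidence of disease progression according to the IWCLL criteria" and then lists nodes, liver or spleen, transformation and lymphocyte count.
- Section 11.235 adds that "In the absence of progression as defined by 1, 2, 3, or 4 above", a hemoglobin fall of at least 2 g/dL or a fall of at least 50% in platelets or neutrophils "will NOT exclude a patient from continuing the study". It suggests a work-up for autoimmune causes and red cell aplasia.
- Footnote 6 of the Section 11.4 table repeats the rule ("In the absence of other indices of clinical progression, the presence of a ≥ 2 g/dL decrease in hemoglobin" and so on). It encourages, but does not require, a marrow examination to separate treatment effect from disease.
- The symptoms row of that table, whose last two columns are PR and PD, reads "Symptoms None None None None N/A N/A".
- Section 11.24 makes stable disease the default, and Section 11.25 scores patients as not progressed by reference to 11.23.

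Section 16.323 counts documented progression or death as the PFS event. Patients who start new CLL treatment before progression are censored at their last prior assessment.

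**The concern.** PFS in each cohort needs one rule for what counts as progression and on what date. For patients with drug-related lymphocytosis the protocol gives two answers. Neither 11.235 nor footnote 6 says what status to record when the work-up shows that CLL caused the falling counts. Section 8.0 expects this situation, since it notes that deteriorating counts may reflect marrow failure from the disease itself. Appendix IV treats progressive marrow failure and constitutional symptoms as active disease.

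Two assessors who each follow the protocol could therefore give one patient different statuses and different PFS dates. Under 11.23 the event is missed, dated late, or replaced by censoring when new therapy starts. That censoring would be tied to the outcome.

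**Working it through.** **Tracing the rules.** In each case the lymphocytosis is accepted as an ibrutinib effect. Section 11.0 then says it is not progression, so the lymphocyte item (11.234) is taken as unmet.

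| Patient with drug-related lymphocytosis | Under 11.0 / 9.4 | Under 11.22–11.24 and the 11.4 table |
|---|---|---|
| A. Nodes and spleen stable; hemoglobin down at least 2 g/dL; work-up attributes this to CLL | Progression: one feature suffices in 11.0; 9.4 lists it | None of the four items met; 11.235 sets the fall aside; stable disease by 11.24 |
| B. As A, but nodes and spleen, both abnormal at baseline, halve; neutrophils above 1500/µL | Progression, as in A | 11.221 not applicable; 11.222 and 11.223 supply two features and 11.224 the count line; PR if held 2 months |
| C. B symptoms for more than 2 months, nothing else | Sign of progression in 9.4; not named in 11.0 | Not in 11.23; N/A for PD in the table; stable disease |

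In A and B the PFS event falls at the cytopenia under the first reading. Under the second it waits for one of the four items or death, or is censored under 16.323. In C the conflict is with 9.4 only.

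**Limit of the conflict.** Sections 9.4 and 11.0 speak only to patients with treatment-related lymphocytosis. A patient whose lymphocytes have halved while hemoglobin falls is outside both, so no contradiction arises.

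**How many patients could be in scope.** Section 1.2 reports lymphocytosis in about 69–75% of CLL/SLL patients on ibrutinib alone, 55% with ofatumumab and 27% with BR. Applying 27–75%:

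- Cohort 1: 0.27 × 22 = 5.9 to 0.75 × 22 = 16.5 patients.
- Cohort 2: 0.27 × 26 = 7.0 to 0.75 × 26 = 19.5 patients.

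These patients could meet the conflict; they are not the number who would. Section 9.4 says it is unknown whether lymphocytosis will occur after daratumumab. Section 1.2 gives median resolution of 18.7 weeks in CLL/SLL, so the conflict would lie mostly in the first months of combination therapy.

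**The plan's own figures.** None is given for PFS. The response-rate designs reproduce and are not challenged:

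- At least 3 of 22: P = 0.0948 at a 5% rate and 0.8455 at 20% (plan: 0.09 and 0.85).
- At least 17 of 26: P = 0.0843 at 50% and 0.9091 at 75% (plan: 0.08 and 0.91).

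**Illustration of direction.** The documents do not say what share q of progressions shows only by cytopenia or symptoms. As assumptions, take q = 5–30%, exponential PFS, and 75% at 26 months (the ibrutinib study in Section 1.2).

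- Events never scored: observed PFS = 0.75^(1−q), which is 76.1%, 77.2%, 79.4% and 81.8% for q = 5, 10, 20 and 30%.
- Events scored d months late: observed PFS = 1 − [(1−q)F(26) + qF(26−d)], with F(t) = 1 − 0.75^(t/26). This runs from 75.1% (q = 5%, d = 3) to 78.2% (q = 30%, d = 12).

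The upper values are generous, because lymphocytosis usually resolves well before 26 months.

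**The case against.** The strongest reply is that 11.23 alone governs. It is the section headed progression, and 7.9a, 11.25 and footnote 6 all point to it. Section 9.4 is supportive-care text, its cytopenia item is qualified by the IWCLL indication for treatment, and 11.0 quotes a workshop report on continuing therapy. This makes 11.23 the likelier default. It does not remove the conflict: 11.0 is current text in the response-evaluation chapter and speaks directly about progression.

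It can also be said that 11.235 concerns staying on study and names no objective status. That is literally so, but 11.23 ties continuing to the absence of progression, so in practice the sentence works as not progressed. For symptoms the point is weaker: they are left out by omission and an N/A entry, not by an express sentence.

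A third reply is that once CLL cytopenia appears, the protection for lymphocytosis lapses and 11.234 itself records progression. That is possible if the rise is no longer accepted as drug effect. Where it is accepted, item 4 is unmet and 11.235 applies.

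Stronger readings are tempting but unsupported:

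- **That reported PFS is overstated overall.** 11.234 exempts infection and tumor flare but does not name ibrutinib lymphocytosis, so some drug effect could be scored as progression. That error would shorten PFS.
- **That the primary response rate is inflated.** Patient B shows that the rules permit a disputed PR, but no frequency is available. The one-of-three-counts rule for PR is stated consistently in 11.22 and footnote 5.
- **That CLL-attributed falls must count as progression or bar PR.** That would choose a rule tied to stopping treatment, which the documents do not settle.

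**Conclusion.** The contradiction stands for patients whose lymphocytosis is accepted as an ibrutinib effect. CLL-attributed anemia or thrombocytopenia is progression under 11.0 and 9.4, and stable disease or PR under 11.22–11.24. Persistent B symptoms conflict between 9.4 and the 11.4 table.

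Taken alone, following 11.23 moves PFS upward. The illustrated change in 26-month PFS, about 0.1 to 6.8 percentage points (75.1 − 75.0 to 81.8 − 75.0), rests entirely on the assumed q and delay and is not an estimate. Neither the size nor the net bias can be derived from the documents. In these cohorts a single reclassified patient is 1/22 = 4.5% or 1/26 = 3.8%.

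PFS is secondary, described by Kaplan-Meier without a test or margin, so no error rate or sample size changes. The matter should be settled before analysis because it affects event dating in both cohorts.

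**What to change.** Reconcile Sections 9.4, 11.0, 11.23 with 11.235, and the Section 11.4 table with footnote 6 into one definition of progression for objective status and PFS. It should state:

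- how a fall meeting the 11.235 thresholds is recorded when the work-up attributes it to CLL;
- how B symptoms beyond 2 months are recorded;
- how each bears on PR.

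Which clinical rule is right, and whether treatment continues, is for the sponsor to reconcile.

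Add one sensitivity analysis to Section 16.323: PFS with and without these events, each with its own event dates.

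The cost is wording in four places and one extra Kaplan-Meier curve per cohort. Blood counts are already scheduled before each cycle during treatment (Section 4.1, footnote 5), but Section 4.2 lists none afterwards, so the analysis covers the treatment period only. Section 11.22 asks for the presence or absence of constitutional symptoms; applying a 2-month criterion also needs an onset date. The main downside is that attribution to CLL takes judgement and the marrow examination is not mandatory, so it will not be uniform. Showing both versions makes that visible.

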
considered standard of care. See detailed section on the MRD (see Section 11.3).

8. Flow cytometry-CLL Panel: The objective of this is to confirm diagnosis as per standard of care (pretreatment). Patients who have a flow cytometry done at any time prior to starting the clinical trial which validates the diagnosis of B-CLL will not be required to have it repeated.
9. **Bone marrow biopsy/aspirate:** At baseline documentation of bone marrow assessment (aspirate and biopsy) will be required to determine the extent of marrow involvement. This is standard of care as per the IWCLL guidelines to accurately assess response to treatment. During study treatment and at the end of treatment, a repeat bone marrow biopsy will only be required to establish the response of complete remission as recommended by the IWCLL guidelines and this will be at the discretion of the treating physician who will determine the appropriate timing based on clinical response assessment (this is consistent with the IWCLL guidelines and is standard of care to). Bone marrow aspirate will be done for assessment of MRD and the timing of this will be followed as noted in detail in foot note 8.
10. FISH (*fluorescent in situ hybridization*) in blood or bone marrow (if no CLL cells in the blood): May be performed any time prior to initiation of therapy. If already done previously, the results will be obtained and recorded, repeat testing will not be needed unless clinically indicated and at the discretion of the treating physician. The FISH panel will include the standard CLL related genomic aberrations including del 17p, del 11q, del 13q, +12.
11. These tests may be performed any time prior to initiation of therapy. If already done previously (prior to initial induction therapy), the results will be obtained and recorded, repeat testing will not be needed unless clinically indicated and at the discretion of the treating physician.
12. Only for patients with Gilbert's syndrome and the total bilirubin >1.5 mg/dL.
13. For women of childbearing potential only. Must be done \leq 14 days prior to registration. NOTE: If the urine test is positive or cannot be confirmed as negative, a serum pregnancy test will be required.
14. After Cycle 7, patients may return every 3 cycles at PI's discretion. Daratumumab subjects will need to return every cycle to get their dara injections.
15. Not required for patients ending treatment due to progressive disease.

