NOTE: In a patient who achieves clinical and laboratory evidence of a complete response, the objective status should be recorded as a CCR on the cycle where the formal response evaluation occurred until a bone marrow biopsy and aspirate have been performed. At that time, the objective status should be amended to classify the patient as a CR, CRi, or nPR **on the cycle where the formal response evaluation occurred**.

11.216 Patients who have clinical and laboratory evidence of CR but who have not yet had a bone marrow biopsy to distinguish between CR and nPR will be classified as having a **Complete Clinical Response (CCR)** until the marrow biopsy is obtained. Patients must meet all of the blood count parameters listed in section 11.214.

11.217 In some settings MRD assays may be considered as a surrogate of response as discussed in section 11.3. No other laboratory assays (e.g., quantitative immunoglobulins) will be used currently as an index for response but will be recorded for clinical correlations.

11.218 For patients whose only measurable disease at the time of enrollment is on CT scan (i.e. SLL with no palpable nodes), a CT scan showing absence of lymphadenopathy (e.g. lymph nodes >1.5 cm) is required before classifying patients a CR.

11.22 **PARTIAL RESPONSE (PR)** requires the patient exhibits at least two of the features in Sections 11.221, 11.222, and 11.223 below (if abnormal prior to therapy) as well as one or more of the remaining features (Sections 11.224, 11.225, 11.226) for at least 2 months. In addition to the parameters listed below, the presence or absence of constitutional symptoms will be recorded.

11.221 $\geq 50\%$ decrease in peripheral blood lymphocyte count from the pretreatment baseline value. Note: This criteria will not be applicable if patients are experiencing ibrutinib associated lymphocytosis as noted above in section 11.0. (LRF workshop)⁶²

11.222 $\geq 50\%$ reduction in the sum of the products of the maximal perpendicular diameters of the largest measured node or nodal masses in the right and left cervical, axillary, and inguinal lymph node regions on physical examination.

11.223 $\geq 50\%$ reduction in size of liver and/or spleen as measured by physical exam noting the maximal distance below the respective costal margins of palpable hepatosplenomegaly during rest.

11.224 Neutrophils $>1500/\mu\text{l}$ or 50% improvement over baseline.

11.225 Platelets $>100,000/\mu\text{l}$ or 50% increase over baseline.

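### The relapse definition in 11.236 does not name CCR, so a limited set of identical regrowths counts as a PFS event or not depending on whether the marrow was done

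*Combined protocol and SAP*

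**What the plan says.** Section 11.236 states: "For patients who achieve a CR or nodular PR, progression will be defined as recurrence of circulating leukemia cell clone" together with an ALC above 5000, "or recurrence of adenopathy >1.5 cm not due to a tumor flare". It asks for no percentage rise, no minimum number of nodes and no repeat determination.

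The general criteria are stricter in several respects:

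- 11.231, first limb: a rise of at least 50%, specifically an "increase in the sum of the products of at least 2 lymph nodes on 2 consecutive determinations 2 weeks apart", where "at least one node must be ≥ 2 cm".
- 11.231, second limb: "or the appearance of new palpable lymph nodes >1.5 cm not due to a tumor flare".
- 11.232: enlargement or new appearance of liver or spleen.
- 11.233: transformation.
- 11.234: a lymphocyte rise of at least 50%, "taking as reference for progressive disease the smallest absolute lymphocyte count recorded since the treatment started", with an ALC of at least 5000.

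Section 11.216 assigns CCR to patients "who have clinical and laboratory evidence of CR but who have not yet had a bone marrow biopsy". They must meet every blood-count criterion in 11.214. Sections 11.24, 13.1 and 16.311 list CCR and CRi as statuses in their own right, and 16.311 counts both as responses. On the repeat marrow, footnote 9 of the test schedule (4.1) says "this will be at the discretion of the treating physician who will determine the appropriate timing". Section 11.215 and note 1 to the table in 11.4 say it should follow within two months.

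Section 16.323 runs PFS from registration to documented progression or death. It does not say which progression rule applies to which response status.

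**The concern.** CCR and CR describe the same clinical remission. The only thing separating them is a procedure whose performance and timing rest partly with the treating physician. If 11.236 is applied as written, two patients with the same nodes and the same counts can have different PFS outcomes because one had a marrow and the other did not.

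The omission also sits oddly beside nPR. An nPR patient needs only one of the three count parameters (neutrophils, platelets, hemoglobin) yet is covered by 11.236. A CCR patient meets all three and is not. The plan gives no reason.

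Section 11.21 further provides that, once the marrow is done, the status is amended on the cycle of the formal evaluation. The applicable progression rule can therefore change in retrospect. What is at stake is the event status or event date of some patients in the Kaplan-Meier estimate of each cohort.

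**Working it through.** The plan states no figure on this point to reproduce. The check applies both rules to the same regrowth in a patient who meets the clinical criteria shared by CR and CCR. The individual node sizes and counts are illustrative assumptions.

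**Inputs.** ALC in CR and CCR is below 4000 (11.214, table in 11.4). Nodes in CCR and nPR may remain up to 1.5 cm (note 7 to the table in 11.4), so a palpable residual node is allowed and its regrowth need not be a new node. The other thresholds are those of 11.231, 11.234 and 11.236.

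**Lymphocytes.** Section 11.234 is met at max(5000, 1.5 × nadir); 11.236 is met above 5000 if the clone has recurred. The rules part only if 1.5 × nadir > 5000, that is nadir > 5000/1.5 = 3,333.

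- Nadir 3,333 or lower: both trigger at about 5000, so there is no gap.
- Nadir 3,500: 11.234 needs 5,250.
- Nadir 3,800: 11.234 needs 5,700. A clonal ALC of 5,400 (5,400/3,800 = 1.42, a 42% rise) meets 11.236 only.
- Nadir 3,999: 11.234 needs 5,998.5.

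The gap therefore needs a nadir of 3,334-3,999 and a clonal ALC above 5000 but below 1.5 times that nadir.

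**Nodes that stayed palpable (cm; change in sum of products).**

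| Regrowth | Change | 11.236 | 11.231 |
|---|---|---|---|
| Two nodes, 1.4×1.4 to 1.6×1.6 | 3.92 to 5.12, +31% | PD | not PD: below 50%, none ≥2 |
| Two nodes, 1.5×1.5 to 1.9×1.9 | 4.50 to 7.22, +60% | PD | not PD: none ≥2 |
| Two nodes, 1.2×1.2 to 1.8×1.8 | 2.88 to 6.48, +125% | PD | not PD: none ≥2 |
| One node, 1.4×1.4 to 3.0×3.0 | 1.96 to 9.00, +359% | PD | not PD by the letter: single node |
| Two nodes, 1.4×1.4 to 2.1×2.1 | 3.92 to 8.82, +125% | PD | PD, after a second determination 2 weeks apart |
| Any newly palpable node >1.5 | n/a | PD | PD |

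**Liver and spleen.** Section 11.236 has no organ criterion. If it replaces 11.231-11.234, new hepatosplenomegaly is progression for a CCR patient (11.232) but not for a CR or nPR patient. Here the difference runs the other way.

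**The case against.** The strongest reply is that CCR is meant to be temporary. The marrow should follow within two months, the status is then amended, and footnote 9 makes the marrow a requirement for establishing CR. The general criteria also already catch any new palpable node above 1.5 cm and most lymphocyte relapses. The table in 11.4 lists CCR nodes as none, so some assessors would call any node above 1.5 cm new. Section 11.0 says ibrutinib-related lymphocytosis without other signs is not progression, which narrows the lymphocyte gap further.

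Much of this stands, and it limits the size of the problem. It does not remove it. Nothing says which rule governs a patient whose marrow is never done, and note 7 does allow a residual node up to 1.5 cm.

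A reader might also treat CRi as excluded in the same way. The documents do not support that firmly. CRi is defined as meeting all CR criteria apart from drug-related cytopenia or a hypocellular marrow, so it can be read as lying within CR, and it does not turn on a missing biopsy. What remains for CRi is an ambiguity to settle.

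**Conclusion.** The point holds in a limited form. Section 11.236 leaves CCR out, leaves CRi unclear, and does not say whether it supplements or replaces 11.231-11.234. For patients who stay CCR, the specific nodal and lymphocyte patterns worked through above are PFS events under one rule and not under the other.

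Three stronger inferences are tempting but unsupported:

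- **That every CCR or CRi patient is affected.** Most relapses are progression under both rules. The documents give no CCR or biopsy rate. If, purely as an assumption, 10-20% of the 48 evaluable patients (22 + 26) reached this depth and half had no marrow, 48 × 0.10 × 0.5 = 2.4 to 48 × 0.20 × 0.5 = 4.8 patients would be judged under the general criteria. Those misclassified would be only the subset with the patterns above.
- **That PFS is uniformly biased upward.** In the nodal and lymphocyte cases the general criteria are harder to meet, which lengthens PFS. The liver and spleen case goes the other way if 11.236 is a replacement.
- **That progression is called at least one formal evaluation later.** Sections 11.0, 11.1 and 11.25 also record PD versus Not PD on cycles without a formal evaluation, so the next opportunity can come after one 28-day cycle.

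PFS is estimated by cohort without a test. The primary endpoint, decision rules and sample size do not depend on 11.236.

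**What to change.** For the PFS analysis, add a sentence to 16.323: the 11.236 relapse definition applies to patients in CR, CRi, CCR or nPR alike, whether or not a marrow was done, and in addition to 11.231-11.234. The words on addition matter, because extending 11.236 as a replacement would take the liver and spleen criterion (11.232) away from more patients.

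Progression also governs stopping of treatment (7.9a, 13.2). For that purpose the point is only that 11.236 and 11.231-11.234 must be reconciled.

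The cost is a few words, best added before PFS is analysed. No new procedure or data item is needed. The downside is that PFS may come out slightly shorter.
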